#### Serious Adverse Event/Experience

A Serious Adverse Event/Experience is any adverse experience occurring at any dose that results in any of the following outcomes:

- Death;
- A life-threatening adverse drug experience;
- Inpatient hospitalization or prolongation of existing hospitalization;
- A persistent or significant disability/incapacity;
- Congenital anomaly/birth defect;
- An important medical event that may require medical or surgical intervention to prevent one of the previously listed outcomes.

#### Unexpected Adverse Event/Experience

An Unexpected Adverse Event/Experience is any adverse drug event/experience not listed in the current labeling for the test product or the current IB. Where test product labeling or IB is not available, anticipated experiences will be based on the known pharmacological/toxicological properties of the test product or ingredients.

#### Follow-up:

If an adverse event/experience occurs, the subject under the direction of the PI or designated sub-investigator trained by the PI may be referred to the nearest acute care facility for treatment. Serious or Unexpected Drug Event/Experience will be followed to resolution. Any adverse event will be documented on an Adverse Event Report Form.

#### Recording and Reporting

The PI or designee records all adverse events on an Adverse Event Form in the subject's CRF.

The PI must promptly report all treatment related adverse events to the PDI study monitor.

All SAE must be reported to the:

- Sponsor within 24 hours of the PI awareness/notification of the event.
- IRB/IEC within 10 working days of the PI awareness/notification of the event.

If a subject has no adverse event during the study, the absence of such must be recorded on the CRF.

## 9 Statistics

### 9.1 Data sets analyzed

Subjects with treatment day baseline bacterial count in the range of 3.11 to 5.50  $\log_{10}/\text{cm}^2$ , inclusive, on the abdomen and 5.00 to 7.50  $\log_{10}/\text{cm}^2$ , inclusive, on the groin will be included in the analysis.

### 9.2 Sample Size

This evaluation will be performed with an estimated of a minimum of 75 evaluable subjects corresponding to 50 evaluable sites per product with qualifying treatment day microbial baseline counts per body area (abdomen and groin). No sample size calculation was performed to provide statistically-powered evidence of efficacy as part of this study.

### 9.3 Efficacy Analyses

An alpha level of 5% will be used for all analyses.

The following descriptive statistics for  $\log_{10}$  CFU/cm^2 and for  $\log_{10}$  CFU/cm^2 reductions from Baseline will be computed for each treatment, grouped by body area and each post application sampling time point (30 seconds, 10 minutes and 6 hours): mean, median, standard deviation, minimum, maximum, and count.

#### 9.3.1 Efficacy Analysis

A linear regression model for each body area (abdomen and groin) and each post treatment sampling time point of immediate efficacy (30 seconds and 10 minutes post-application) will be used. In the model, the dependent variable used will be the post treatment bacterial count ( $\log_{10}$  CFU/cm^2) and predictors will be the treatment as a fixed effect and the Baseline as a covariate. The ATE corrected for Baseline will be estimated from the model and compared to non-inferiority criteria.

To evaluate the persistent efficacy (6 hours post-application) of the product A and B, microbial counts ( $\log_{10}$  CFU/cm^2) at 6 hours post-application for each product application site will be converted to a binary (success/failure), "success" defined as having microbial counts less than or equal to the baseline counts. Responder rates at 6 hours post product application will be summarized descriptively for each product on each body area.

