## 2 Study Objectives

### 2.1 Efficacy objectives

The objective of this study is to demonstrate immediate (30 seconds and 10 minutes) and persistent (6 hours) antimicrobial efficacy for patient preoperative skin preparation of product A and product B compared with product C.

To demonstrate the immediate antimicrobial efficacy at 30 seconds and 10 minutes post-application the following criteria should be met on both body area (abdomen and groin):

- non-inferiority of the ATE of the product A and product B compared to product C (the upper two-sided 95% confidence bound of the post-application microbial counts corrected for Baseline of the A-C or B-C should be less than  $0.5 \log_{10}$ ).

To demonstrate the persistent efficacy for patient preoperative skin preparation, the microbial counts ( $\log_{10}$  CFU/cm^2) at 6 hours post-application should be lower than or equal to the baseline for 100 percent of the subjects in each body area.

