#### **3.3 Randomization and Blinding**

The randomization scheme for the study will be provided by the Research facility.

Each subject will receive two treatments per body area. Assignment of products to the left or right side for each body area will be per a computer-generated randomization schedule.

Specific sites of sampling for baseline and post application sampling time points will be randomized on each body site (abdomen/groin and left/right).

Randomization will continue until required number of subjects with required treatment day baseline counts is enrolled.

The PI is responsible for ensuring that the randomization is followed. The randomization schedule for the abdominal and groin sites will be provided in a separate document. The study products will be labeled with the appropriate codes as designated by the study randomization.

Each subject will be identified by their initials and a subject number for which they qualify. Inclusion subject numbers will not be assigned until a subject has passed the screening criteria, including screening bacterial counts.

- Screening subjects will be assigned numbers starting with 001 and the letter "P": P001
- Treatment subjects will be assigned numbers with 001 and the letter "I": I001

The study products will not be blinded from the PI or other study staff performing the study material application or bacterial sample collections. The staff member(s) performing bacterial enumeration will be blinded from the identification of treatment assignment. The study staff performing the bacterial enumeration will not be involved in the study products application or the collection of samples. The Raw Data Sheet sections of the CRF will be maintained separately (from the pages within the CRF which include study treatment identifications) during the conduct phase of the study. The study staff performing the bacterial enumeration will record counts directly onto the Raw Data Sheet pages of the CRF without accessing the subject study documentation folder containing the other CRF pages. The Raw Data Sheets will be compiled with the entire CRF after all data recording have been completed.

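### The efficacy regression ignores that sites come in pairs from the same subject, so the confidence bound that decides non-inferiority has the wrong width

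*Combined protocol and SAP*

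**What the plan says.** Section 3.3 sets a within-subject design: "Each subject will receive two treatments per body area", and "Assignment of products to the left or right side for each body area will be per a computer-generated randomization schedule". Section 9.2 plans "a minimum of 75 evaluable subjects corresponding to 50 evaluable sites per product" in each body area and adds: "No sample size calculation was performed to provide statistically-powered evidence of efficacy as part of this study".

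Section 9.3.1 specifies the immediate-efficacy analysis as "A linear regression model for each body area (abdomen and groin) and each post treatment sampling time point of immediate efficacy", in which "predictors will be the treatment as a fixed effect and the Baseline as a covariate". The Synopsis gives the same model. Under Section 2.1, immediate efficacy is shown if "the upper two-sided 95% confidence bound of the post-application microbial counts corrected for Baseline of the A-C or B-C should be less than" 0.5 log10, on both the abdomen and the groin, at 30 seconds and 10 minutes. Section 9.3 states: "An alpha level of 5% will be used for all analyses". The 6-hour responder rates are only summarised descriptively, so these bounds are the only model-based inference on efficacy.

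Neither the Synopsis nor Section 9 mentions a subject effect, a within-subject covariance structure or a cluster-robust variance. The split of subjects across the product pairs AB, AC and BC is not given; the randomisation schedule is a separate document.

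**The concern.** With three products and two sites per subject in each body area, this is an incomplete block design with the subject as the block. The A-C and B-C contrasts are therefore partly within-subject. The planned regression treats a subject's two sites as if they came from two different people.

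If the two sites remain positively correlated after baseline adjustment, two things follow. The reported standard error is too large for the estimate it accompanies, so the nominal 95% interval covers more than 95%. The estimate is also inefficient, because it gives within-subject and between-subject comparisons the same weight. The verdict rests on where one confidence limit falls relative to 0.5 log10, so a non-inferior product could miss the criterion because of the model alone.

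**Working it through.** **The plan's own figure.** 75 subjects × 2 sites ÷ 3 products = 50 sites per product, as in Section 9.2. The count works only because every subject contributes two sites, so each model has 150 observations in 75 pairs.

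**Inputs from the documents.** 50 sites per product; margin 0.5 log10; two-sided 95% limits, hence 2.5% on the upper bound.

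**Assumptions.** The documents give no SD and no correlation. Let *s* be the residual SD and ρ the correlation between a subject's two sites after baseline adjustment. Assume 25 subjects per product pair, complete pairs and, for the mixed model, known ρ. B-C gives the same results as A-C under this balance.

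**Formulas for A-C, in units of *s*².**
- Variance reported by the planned regression: 2/50 = 0.04, so SE = 0.200*s*.
- True variance of that estimate: 25 subjects contribute to both the A and the C mean, so the covariance of the two means is 25ρ/50² = 0.01ρ. The variance is 0.04 − 0.02ρ = 0.04(1 − ρ/2).
- Mixed model (three products, blocks of two, 50 replicates, efficiency 0.75): precision = 37.5/[2(1 − ρ)] + 12.5/[2(1 + ρ)].
- At ρ = 0.5: the true SE is √(0.04 × 0.75) = 0.173*s*. The mixed-model precision is 37.5 + 4.167 = 41.67, so its SE is 0.155*s*.
- One-sided error at the margin: Φ(−1.96 × 0.200 ÷ true SE).

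| ρ | Planned SE | True SE of same estimate | Mixed-model SE | Planned ÷ true | Planned ÷ mixed | One-sided error at margin |
|---|---|---|---|---|---|---|
| 0 | 0.200 | 0.200 | 0.200 | 1.00 | 1.00 | 2.5% |
| 0.1 | 0.200 | 0.195 | 0.194 | 1.03 | 1.03 | 2.2% |
| 0.3 | 0.200 | 0.184 | 0.178 | 1.08 | 1.12 | 1.7% |
| 0.5 | 0.200 | 0.173 | 0.155 | 1.15 | 1.29 | 1.2% |
| 0.7 | 0.200 | 0.161 | 0.123 | 1.24 | 1.63 | 0.75% |

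A simulation of the planned regression with a baseline covariate (5000 runs per ρ) gave error rates at the margin of 2.7%, 1.5%, 1.1% and 0.8% for ρ = 0, 0.3, 0.5 and 0.7, in line with the formula.

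**Power per comparison, true difference 0.** Planned: Φ[(0.5 − 1.96 × 0.200*s*) ÷ (true SE × *s*)]. Mixed model: the same expression with the mixed-model SE in both places.

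| Assumed SD | ρ = 0 (both models) | ρ = 0.3, planned / mixed | ρ = 0.5, planned / mixed | ρ = 0.7, planned / mixed |
|---|---|---|---|---|
| 0.6 | 99% | 99% / >99% | 99% / >99% | >99% / >99% |
| 0.8 | 88% | 90% / 94% | 91% / 98% | 93% / >99% |
| 1.0 | 71% | 72% / 80% | 73% / 90% | 75% / 98% |
| 1.2 | 55% | 55% / 65% | 56% / 77% | 56% / 92% |
| 1.5 | 38% | 38% / 47% | 37% / 58% | 36% / 77% |

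At SD 1.0 the 95% half-width is 0.392 as planned, against 0.349, 0.304 and 0.241 with a subject effect at ρ = 0.3, 0.5 and 0.7.

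**Unbalanced split.** With an assumed 35 AB, 15 AC and 25 BC subjects and ρ = 0.5, the planned SE of A-C is 0.212*s*, its true SE 0.194*s* and the mixed-model SE 0.170*s*. The planned interval is still 10% too wide for its own estimate and 25% wider than the mixed-model interval.

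**The case against.** The strongest reply is that the error is on the safe side. With positive correlation the one-sided error at the margin falls below 2.5%, so a pass under the planned regression would remain valid. The cost is lost power, and Section 9.2 claims no power. All of this is correct, and it limits the consequence to a product failing when it should pass. It does not make the interval right. Because no power calculation was done, there is also no documented reserve to absorb the loss.

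The size is also unknown. The relevant correlation is what remains after each site's own baseline is adjusted for, and it could be low. At ρ = 0.1 the interval is under 3% too wide; at SD 0.6 both models have power near 100%. Incomplete pairs would reduce the gain. This stands, and is why ranges are shown. Near-zero correlation between two sides of one person, after the same washout and on the same day, would nevertheless be a strong assumption, and the plan does not argue for it.

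It is fair, too, that the planned estimate keeps part of the benefit of pairing: its true SE does fall as ρ rises. The reported bound does not show that gain.

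Finally, Section 1 ties the evaluation to US FDA analysis criteria, and the documents do not show whether those prescribe this regression. That is a reason to retain it as a sensitivity analysis.

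**Conclusion.** The concern holds. The design is paired, the specified model is not, and nothing in the documents bridges the two. With positive within-subject correlation, the bound that decides non-inferiority is wider than its stated level warrants, and considerably wider than the design could deliver: by 12% to 63% over ρ = 0.3 to 0.7 under a balanced split. At an assumed SD of 1.0 and ρ = 0.5, that is the difference between about 73% and 90% power for one comparison.

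Section 2.1 needs four such bounds per product (two body areas, two times), so the loss accumulates. If the four were independent, joint power would be 0.734⁴ ≈ 29% as planned and 0.898⁴ ≈ 65% with a subject effect; correlated results would give higher values, at most the single-comparison figures.

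The direction is conservative for ρ > 0, and there is no error at ρ = 0. SD, ρ and the pair split are assumptions; the absence of a subject term is not.

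**What to change.** In Section 9.3.1 and the Synopsis, replace the regression with a linear mixed model for each body area and each immediate time point: fixed effects for treatment, the site's treatment-day baseline and side (left/right), and a random subject intercept, fitted by REML with Kenward-Roger degrees of freedom. Take A-C and B-C with two-sided 95% limits from this model and compare the upper limits with 0.5 log10 as now. The subject term is the essential part. Side is randomised, so the side effect is optional, and another adequate small-sample method would also serve. A cluster-robust variance on the planned regression would correct the width but would not recover the efficiency.

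State the intended split of subjects across AB, AC and BC. Keep the plain regression as a prespecified sensitivity analysis if wanted.

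The cost is a sentence or two in the plan and a different procedure call. The treatment contrasts and the margin are unchanged, no new data are needed, and subjects with only one evaluable side stay in the analysis, consistent with the no-imputation rule in Section 9.5. The change should be made before the data are analysed; a switch after a near miss would look data-driven.

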### 9.4 Safety Analysis

All treated subjects will be considered evaluable for safety. Skin irritation scores will be reported for any subject who is scored with a 1 or more at any observation (baseline screening day, baseline treatment day, post-application/prior to 30 seconds, 10 minutes, and 6 hours sampling procedures), in any category for any site.

Adverse events (including post treatment skin irritation scores of 3), will also be summarized. Summary tables will present incidence rates of adverse events by treatment group for all subjects who enter the treatment period. Listings of adverse events will be provided.

## **9.5 Procedures for Accounting for Missing, Unused, and Spurious Data**

Missing microbiological data at 30 seconds, 10 minutes, or 6 hours, such as due to laboratory error or subject lost to follow-up, will be reported as missing and will not be imputed. Inclusion of these subjects in the per-protocol data set will be based on the criteria defined above. Details of any missing data and rationale for inclusion/exclusion in the per-protocol data set will be described in the study report.

## **10 PI Responsibilities**

The PI is responsible for ensuring that this clinical investigation is conducted according to this protocol; protecting the rights, safety, and welfare of subjects; and controlling the study products under investigation. The PI has overall responsibility for the technical conduct of the study, as well as for the interpretation, analysis, documentation and reporting of results, and represents the single point of study control.

## **11 Monitoring**

PDI, as sponsor of this study along with the PI, is responsible for ensuring the proper conduct of the study with regard to protocol adherence and validity of the data recorded on the CRFs. PDI has, therefore, assigned a study monitor to this study. The progress of the study will be monitored by:

- Periodic on-site review
- Telephone communications and e-mail
- Review of CRFs and source documents

The PI will give the PDI study monitor direct access to source documents that support data on the CRFs and make available such records to authorized PDI personnel, quality assurance, IRB/IEC, and regulatory personnel for inspection and/or copying.

## **12 Quality Control and Quality Assurance**

PDI, and the PI are responsible for implementing and maintaining Quality Assurance and Quality Control systems through written SOPs to ensure that this study is conducted and data are generated, documented and reported in compliance with the protocol, GCP and regulations cited in [Section 14](#) of this protocol. Study monitoring may be carried out to accomplish this.

## **13 Audits and Inspections**

If the study is selected for audit by the Sponsor or if there is an inspection by the appropriate Health Authorities, then the PI and her team will make themselves available during the visit. The PI must agree to the inspection of all study related records and give the auditor/inspector direct access to source documents for verification of data on CRFs. The subject's anonymity must be safeguarded and data checked during the audit remain confidential.

As soon as the PI is aware of an upcoming inspection/audit by the Health Authorities, she will promptly inform PDI. As agreed with the PI, PDI personnel might be present at the site during the inspection.

## **14 Ethical and Regulatory Standards**

The study will be conducted in compliance with this protocol, the regulatory guidelines of the US FDA regulations, 21 CFR 50 (Protection of Human Subjects), 56 (IRB), the ethical principles of the Declaration of Helsinki, the ICH-GCP Guidelines as currently amended, and all applicable SOPs of ER

The study will start only after approval of the protocol and ICF including Subjects instruction and Subjects calendar (Main study and Neutralization study) by the IRB/IEC. The approval letter or notice must contain the IRB name and identification number, meeting date, and sufficient information to identify the protocol and ICF form by name and number that were reviewed. PDI prior to study initiation, must receive a copy of the IRB/IEC approval letter.

The IRB used for this study will be:

Name: Advarra, Inc

Address: [name]

The IEC used for this study will be:

Name: Institutional ethics committee

Address: [name]

Subject confidentiality is strictly held in trust by the PI, the study staff, and PDI. This confidentiality is extended to cover testing of biological samples in addition to the clinical information relating to participating subjects. Subject confidentiality and anonymity will be maintained at all times by removal of all identifiers from any data, clinical samples or documentation submitted for this study.

Any data collected meeting the definition of protected health information will be collected and maintained using the designated authorizations and following all privacy procedures as specified in the applicable health authority regulations.

PDI will maintain the security and confidentiality of all clinical study data received.

PDI clinical study databases will not be shared with any third party without the express written consent of the PI and/or Research facility.

## **15 Data Handling and Record Keeping**

### **15.1 Completion of Case Report Forms**

The PI or sub-investigator will review all CRF entries for completeness and accuracy. If a correction is required, a single line must be drawn through the error. The person making the correction will initial, date, and provide a reason for the error (if not self-evident).

The PI or sub-investigator must review and sign each CRF in a timely fashion following completion and make them available to the PDI study monitor for monitoring. Before acceptance, the monitor will review the CRFs to ensure accuracy and completeness. The original CRFs will be kept at the Research facility and electronic/scanned copies will be sent to PDI. In addition, any data queries prepared after the original CRFs have been completed must be answered promptly.

## 15.2 Final Clinical Study Report

Final Clinical Study report will be produced by Research facility in collaboration with PDI team.

## 15.3 Records, Reports and Retention Requirements

The PI will maintain study records for a minimum of 10 years following completion of the study. Sponsor will be notified in written regarding the due date of the record retention time.

Records that must be maintained by the PI include, but are not restricted to:

- Signed study protocol, amendments, deviations
- IRB/IEC approval of protocol, ICF including Subjects instruction and Subjects calendar (Main study and Neutralization study)
- Applications to the IRB/IEC
- Signed ICFs
- CRFs
- Adverse event reports
- Records of receipt, use or disposition of the study material
- Correspondence relating to the study
- Investigator Final Report
- Sponsor Final Report (if provided)

No formal presentation or publication of data from this study can be initiated without the sponsor's explicit written agreement and in direct collaboration with the sponsor.

## 17.2 Study Summary

[figure not shown]
### 17.2.1 Main study

Pre-Study Preparation	Screening Phase		Treatment Phase	
	At least 14 Day Restriction Period	Screening Day	Abdominal Region	Groin Region
Staff reviews study protocol	Initiation of consenting process	Complete Screening Inclusion/ Exclusion Criteria form	Complete Treatment Inclusion/ Exclusion Criteria form	
Prepare ICF, Subjects instruction and Subjects calendar (Main study and Neutralization)	Review study ICF and Inclusion/ Exclusion Criteria	Visual skin assessment (abdominal and groin regions)	Visual skin assessment (abdominal and groin regions)	
Obtain IRB/ IEC approval	Review subject instructions	Collect screening baseline samples from abdominal and groin regions	Mark test areas, Collect baseline samples	
Recruit subjects	Subject signs ICF	Count screening plates, determine which subjects qualify for study	Apply test products	
Prepare subject kits	Visual skin assessment (abdominal and groin regions) and Inclusion/ Exclusion Criteria	Contact and enroll eligible subjects, schedule Treatment Day	Visual skin assessment, within 30 seconds post-prep sample	Visual skin assessment, within 30 seconds post-prep sample
Prepare CRFs and appendices to CRFs (Main study and Neutralization)	Dispense subject kits	Schedule for clipping/ re-clipping, if needed, approximately 48-96 hours prior to Treatment Day visit	Visual skin assessment, 10 minutes post-prep sample	Visual skin assessment, 10 minutes post-prep sample
	Schedule for clipping/re-clipping, if needed, approximately 48-96 hours prior to	No bathing / showering 72 hrs. prior to Treatment Day visit	Visual skin assessment, 6 hours post-prep sample	Visual skin assessment, 6 hours post-prep sample
	No bathing / showering 72 hrs. prior to screening visit		Count Treatment Day Baseline plates, determine qualification	Count Treatment Day Baseline plates, determine qualification

